6.4. Per Protocol Set

All participants who received at least 1 dose of ALXN1840, had Baseline and all post-Baseline values of Cu intake (in food and drink) and Cu output (in feces and urine), and were 100% compliant with study drug dosing. Participants with major protocol deviations that are likely to impact the primary endpoint analysis will be excluded from the Per Protocol (PP) Set. Major protocol deviations, and the PP Set, will be defined, documented, and agreed within Alexion prior to database lock.

6.5. Safety Set

All participants who received at least 1 dose of ALXN1840.

6.6. Pharmacokinetic/Pharmacodynamic Analysis Set

All participants who have sufficient samples to enable the calculation of PK parameters and provide PK/PD profiles.

7. STATISTICAL ANALYSIS

Summary statistics will be computed and displayed by day and period (pre-dose Baseline, treatment, steady state, and post-treatment), where applicable. Descriptive statistics for continuous variables will minimally include the number of participants, mean, standard deviation (SD), minimum, median, and maximum. For categorical variables, frequencies and percentages will be presented. Graphical displays will be provided as appropriate.

Analyses will be performed using the SAS[®] (Statistical Analysis Software[®]) software Version 9.4 or higher (SAS Institute Inc., Cary, North Carolina).

In general, analyses will be presented by group (referring to the study being conducted in groups; see Section 4) and overall, where specified.

7.1. Study Participants

7.1.1. Disposition of Participants

The number and percentage of all participants screened, enrolled, and included in the Full Analysis (FA), PP, Safety, and PK/PD analysis sets will be summarized. The reasons for exclusion from the analysis sets will also be provided. Frequency counts and percentages of participants excluded prior to enrollment will be provided for participants who failed to meet study entry requirements during Screening.

The number and percentage of participants who completed, or prematurely discontinued from the study will be summarized by group and overall. For participants who discontinued the study, the number and percentage will be summarized by their reason for premature discontinuation. Additionally, the number of participants who completed or prematurely discontinued treatment and the reason for treatment discontinuation will be summarized. A summary of participants who did not meet inclusion or who met exclusion criteria will be provided.

Descriptive statistics of the number of days in the study will be summarized. The date of first and last use of the study drug, and the study termination date will be listed. Individual reasons for premature discontinuation from the study will be presented in a listing, as will the reason for premature discontinuation from study drug. All enrolled participants will be listed indicating their membership to each analysis set along with the reason for exclusion. Additionally, a listing of the inclusion/exclusion criteria and a listing of participants and the inclusion criteria they failed to meet and the exclusion criteria they met will be provided. A listing of screen failure participants will also be provided.

7.1.2. Protocol Deviations

All important/not important protocol violations will be determined and appropriately categorized prior to database lock. The number and percentage of participants with any important/not important protocol violations as well as the number and percentage of participants with violations within each category will be presented. A listing will also be provided.

7.1.3. Demographics, Baseline Characteristics, and History

All demographic and Baseline characteristics information will be summarized for the FA Set. Summary statistics will be presented by group and overall. Continuous variables will be

presented using descriptive statistics, and categorical variables will be presented using frequencies and percentages. Age will be calculated relative to informed consent and will be summarized as a continuous variable. Listings will also be provided.

7.1.3.1. Demographics

The following demographic variables will be summarized:

- Sex
- Race (where collection is permitted by local regulations)
- Ethnicity (where collection is permitted by local regulations)
- Age (years)
- Height (cm)
- Weight (kg)
- Body mass index (BMI) (kg/m^2)

7.1.3.2. Baseline Characteristics

The following Baseline characteristics will be summarized:

- LBC ($\mu\text{mol}/\text{L}$)
- LBC categorization based on normal reference range (female: $<0.7 \mu\text{mol}/\text{L}$, 0.7 to $5.9 \mu\text{mol}/\text{L}$, $>5.9 \mu\text{mol}/\text{L}$; male: $<0.9 \mu\text{mol}/\text{L}$, 0.9 to $4.4 \mu\text{mol}/\text{L}$, $>4.4 \mu\text{mol}/\text{L}$)
- NCC ($\mu\text{mol}/\text{L}$)
- NCC categorization based on normal reference range ($<0.8 \mu\text{mol}/\text{L}$, 0.8 to $2.3 \mu\text{mol}/\text{L}$, $>2.3 \mu\text{mol}/\text{L}$)
- Albumin (g/L)
- International Normalized Ratio (INR)
- Total bilirubin ($\mu\text{mol}/\text{L}$)
- Direct bilirubin ($\mu\text{mol}/\text{L}$)
- Alanine aminotransferase (ALT) (IU/L)
- Aspartate aminotransferase (AST) (IU/L)
- Gamma-glutamyltransferase (GGT) (IU/L)
- Platelets ($10^9/\text{L}$)
- Leukocytes ($10^9/\text{L}$)
- Creatine Kinase (IU/L)
- Total Plasma Cu ($\mu\text{mol}/\text{L}$)

- Total plasma Cu; categorization based on normal reference range (low: < 11.33 $\mu\text{mol/L}$ [$< 720 \text{ ng/mL}$]; normal: 11.33 - 26.12 $\mu\text{mol/L}$ [$720 - 1660 \text{ ng/mL}$]; high: > 26.12 $\mu\text{mol/L}$ [$> 1660 \text{ ng/mL}$])
- PUF-Cu ($\mu\text{mol/L}$)
- Total plasma Mo ($\mu\text{mol/L}$)
- PUF-Mo ($\mu\text{mol/L}$)
- Cp (mg/L)
- 24-Hour urinary Cu ($\mu\text{g/day}$)
- 24-Hour urinary Mo ($\mu\text{g/day}$)
- Categorization of baseline lab values (ALT, AST, GGT, platelets, leukocytes, creatine kinase) based on the reference ranges (L: Low, N: Normal, H: High)

7.1.3.3. Medical/Surgical History and Physical Examination

Medical and surgical history will be summarized by counts and percentages and displayed by System Organ Class (SOC) and Preferred Term (PT) within each SOC. Both SOCs and PTs will be coded using the most up-to-date version of the Medical Dictionary for Regulatory Activities (MedDRA), Version 22.0 or higher, available at the start of the study. This dictionary will be used throughout the life of the study and will not be updated during the study conduct. The number and percentage of participants will be presented for ongoing conditions and previous conditions separately by SOC and PT. A listing will also be created.

For the physical examination, the number and percentage of participants with abnormal findings at each visit for each body system will be summarized and included in the data listing.

7.1.4. Prior and Concomitant Medications/Therapies

Prior medications will be defined as medications that were discontinued prior to the start of study drug. Concomitant medications will be defined as medications that either started prior to first dose of study drug and were continuing at the time of first dose of study drug or started on or after the date of the first dose of study drug. If it cannot be determined whether a medication was stopped prior to the start of study drug dosing due to partial or missing medication start or end dates, it will be considered a concomitant medication.

The World Health Organization (WHO) Drug Dictionary version from March 2018 or later will be used to code the medications. Medications will be summarized by Anatomical Therapeutic Chemical (ATC) level 3 class and generic drug name.

Prior and concomitant medications will be summarized separately for the FA Set by group and overall. The number and percentage of participants receiving any concomitant medication will be summarized, as well as the number and percentage receiving any concomitant medication by ATC drug class and generic drug name. Participants reporting use of more than 1 medication at each level of summarization (any medication received, ATC class, and generic drug name) will be counted only once. All ATC class terms will be displayed alphabetically and generic drug names within each ATC class will be displayed by descending order of incidence.

Prior and concomitant medications will be presented in a data listing by participant and medication name.

7.2. Efficacy Analyses

No efficacy endpoints are included as part of this study; therefore, there is no analysis of efficacy.

7.3. Copper and Molybdenum Balance Analyses

The primary objective of this study is to assess the change from Baseline in Cu balance over 2 weeks of repeated daily ALXN1840 dosing (ALXN1840 treatment at 30 mg/day in healthy participants). Secondly, the study will also assess whether a net negative Cu balance is achieved following ALXN1840 treatment. The study will also assess Mo balance at ALXN1840 PK steady state.

Copper balance is defined by the difference in Cu input and Cu output. A negative Cu balance will indicate greater Cu output than Cu intake. Copper input is defined as the sum of all Cu input as measured in all food and fluids over the specified period. Copper output will be defined as the sum of all Cu output as measured in urine and feces over the specified collection period. Many of the Cu inputs and outputs will be collected with technical replicates and the mean of the replicates will be utilized in the analysis. Daily balance values may also be calculated. The study assumes insensible Cu/Mo loss due to sweat does not change significantly with ALXN1840 treatment and is therefore not measured.

Molybdenum mass balance is defined as the difference in Mo input and Mo output. It will be calculated in a similar manner as Cu balance and includes the additional Mo intake from ALXN1840. The nominal amount of Mo contained in ALXN1840 will be used and is estimated as 3.33 mg in each 15 mg tablet per the following calculation: 95.96 g/mol (molecular weight of Mo) / 432.54 g/mol (molecular weight of bis-choline tetrathiomolybdate) * 15 mg/tablet = 3.33 mg Mo. Mo mass balance will be calculated at steady state (Day 12 through Day 15) and over the entire Treatment Period (Day 1 through Day 30).

The average daily Cu and Mo balance, and/or change from Baseline in average daily Cu and Mo balance will be calculated using data from the following periods:

- Day -4 through Day -1 representing the Pre-dose Baseline Period (Cu/Mo balance)
- Days 4 through Day 15 representing the 30 mg/day Treatment Period (Cu balance for primary and secondary endpoints)
- Day 1 through Day 15 representing the ALXN1840 30 mg/day Treatment Period (Mo mass balance and Cu as exploratory analyses)
- Days 12 through Day 15 representing the Steady State Treatment Period (steady state Mo/Cu balance)
- Days 1 through Day 30 representing the entire Treatment and Post-treatment Period (total Mo and Cu balance)

As ALXN1840 is expected to increase Cu removal through fecal excretion, Cu in stool will be critical for determining Cu balance. Because stools can be irregular, assessment of Cu and Mo

balance will only include data up to the day of the final bowel movement. For example, if for the Day 1 through Day 15 collection period, the final bowel movement occurs on Day 14, average daily Cu balance for the Day 1 through Day 15 period will only include data averaged from Day 1 through Day 14 (and Day 15 data will be omitted).

In the case of the 30 mg/day Steady State Treatment Period for Mo balance, fecal data collected on Days 16 and 17 may be used if needed to support assessments for the 30 mg/day Mo steady state balance. Use of this fecal data (as needed) is consistent with an approximately 2-day gastrointestinal transit time.

In the case of bowel movement irregularity and to support assessment of Cu output over time, bowel movement Cu and Mo outputs may be averaged over the days between bowel movements (or start of study) to ensure an approximate value for each 24-hour period as needed for calculations. The 24-hour collection period is defined as relative to the first ALXN1840 dose administration.

7.3.1. Primary Analysis

The primary analysis will be performed using the FA Set. Additionally, the primary analysis will be performed on the PP Set. Change from Baseline in average daily Cu balance over Days 4 to 15 will be summarized using descriptive statistics based on data as observed. The 95% confidence limits for the mean change from Baseline will be provided.

7.3.1.1. Handling of Dropouts or Missing Data

Participants who prematurely discontinue from the study will be included up to the time of discontinuation.

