#### **6.6.1.2. Individual Adverse Reaction Rules**

An individual participant will not receive any further dose(s) of ALXN1840, if either of the following occurs:

- Participant experiences any CTCAE Grade 3 (or higher) adverse reaction, or a serious adverse reaction, irrespective of severity/CTCAE grade.
- Participant experiences any CTCAE Grade 1 or 2 adverse reaction considered to be related to ALXN1840 and considered a safety concern by the SRC.

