#### **6.6.1.4. Special individual Adverse Reaction Rules**

Dosing in an individual participant will be suspended if they experience any of the following:

- Liver function test elevation
  - ALT or AST value  $> 3 \times \text{ULN}$  in the presence or absence of symptoms. Grade 2 or higher by NCI CTCAE v 5.0.
  - Any possible Hy's law case will be considered a serious adverse event defined as  $\text{ALT} \geq 3 \times \text{ULN}$  AND total bilirubin  $\geq 2 \times \text{ULN}$  (or 35% increase in direct bilirubin) or  $\text{INR} > 1.5$  (if measured)

- Any ALT or AST or other liver function test elevation or trend in elevation that in the opinion of the Investigator and/or Alexion may place the participant at risk if dosing is continued
- Hematology
  - Hemoglobin reduction to an absolute value of 9.5 g/dL (95 g/L) or lower. Because of the repeated blood draws in the study, an addition 0.5 g/dL (5 g/L) over the Grade 2 CTCAE v 5.0 value may be tolerated at the investigator discretion and based on clinical judgment.
  - Platelet count reduction to an absolute value < 75,000/mm^3, defined as Grade 2 or higher by NCI CTCAE v 5.0
  - Any hematologic abnormality that in the opinion of the investigator and Alexion may place the participant at risk if dosing is continued
- QT interval prolongation
  - A prolongation of the QTcF interval of > 500 ms (using consistent, technically valid triplicate ECG)

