## 7. DISCONTINUATION OF STUDY INTERVENTION AND PARTICIPANT DISCONTINUATION/WITHDRAWAL

### 7.1. Discontinuation of Study Intervention

In rare instances, it may be necessary for a participant to permanently discontinue (definitive discontinuation) the study intervention. If the study intervention is definitively discontinued, the participant should remain in the study to be evaluated for safety follow-up. See the SoA for data to be collected at the time of discontinuation of study intervention and follow-up and for any further evaluations that need to be completed.

Discontinuation of study intervention for abnormal liver function should be considered by the investigator when a participant meets one of the conditions outlined in the Dose Modification criteria ([Section 6.6](#)) or if the Investigator believes that it is in best interest of the participant.

If a clinically significant finding is identified (including, but not limited to changes from baseline in QT interval corrected using Fridericia's formula [QTcF]) after enrollment, the Investigator or qualified designee will determine if the participant can continue in the study and if any change in participant management is needed. This review of the ECG printed at the time of collection must be documented. Any new clinically relevant finding should be reported as an AE.

Participants must be considered for discontinuation from intervention if any of the following occur during the study:

- Serious hypersensitivity reaction;
- Severe uncontrolled infection;
- Use of disallowed medication;
- Pregnancy or planned pregnancy (see [Section 8.2.6](#)); or
- Alexion or the Investigator deems it is necessary for the participant.

See the SoA ([Table 1](#)) for samples and data to be collected at the time of study intervention discontinuation and follow-up and for any further evaluations that need to be completed.

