#### **8.2.4.1. Bowel and Urine Monitoring**

Participants' bowel movements and urination will be monitored by the clinical staff. The clinical staff will record each time a fecal and urine sample is collected in the CRF. All urine and feces must be collected from Day -4 through Day 30. Day -4 through Day -1 will represent the pretreatment baseline, Day 1-15 will represent the treatment period and Day 16-30 will represent the post-treatment period.

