7.3.2. Secondary Analyses

Secondary analyses will be performed using the FA Set. The secondary continuous endpoints (Cu balance, Mo balance, urinary excretion, etc.) will be analyzed using the same methods described for the primary analysis. The periods of interest described in Section 7.3 will be utilized as appropriate. The daily Cu and Mo balances for each participant will be plotted, as will the mean daily Cu and Mo balances.

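### The SAP has no rule for balance data collected after ALXN1840 is stopped in participants who stay in the study, and the steady-state Mo/Cu and net Cu summaries have no on-treatment check

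*SAP*

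**What the plan says.** **Dropout rule.** SAP 7.3.1.1 is one sentence: "Participants who prematurely discontinue from the study will be included up to the time of discontinuation". It is triggered by leaving the study, not by stopping drug.

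**Stopping drug is a separate event.** Protocol 6.6.1.2 provides that "An individual participant will not receive any further dose(s) of ALXN1840, if either of the following occurs", and Protocol 6.6.1.4 that "Dosing in an individual participant will be suspended if they experience any of the following" (liver, hematology and QT triggers). Protocol 7.1 adds: "If the study intervention is definitively discontinued, the participant should remain in the study to be evaluated for safety follow-up".

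**Collection.** Protocol 8.2.4.1 states "All urine and feces must be collected from Day -4 through Day 30", with no exception for participants no longer dosed.

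**Windows.** SAP 7.3 fixes them by calendar day: "Days 4 through Day 15 representing the 30 mg/day Treatment Period (Cu balance for primary and secondary endpoints") and "Days 12 through Day 15 representing the Steady State Treatment Period (steady state Mo/Cu balance").

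**Analysis sets.** The FA Set requires one dose (SAP 6.3). The primary analysis uses the FA Set with data as observed and is repeated on the PP Set (SAP 7.3.1), which under SAP 6.4 requires full dosing compliance. For the rest, "Secondary analyses will be performed using the FA Set" (SAP 7.3.2). SAP 7.3.1.5 plans no sensitivity analyses.

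**The concern.** The endpoints are worded as balance during ALXN1840 treatment and Mo balance at PK steady state. A participant whose last dose was on Day 8 is in washout on Days 12-15: no drug Mo goes in while Mo from earlier doses is still coming out. Averaging that participant into the steady-state summary gives a negative value that does not measure the stated endpoint. For Cu, days after the drug effect has faded pull the treatment-period mean towards baseline.

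The SAP recognises this situation elsewhere. SAP 7.1.1 tabulates treatment discontinuation apart from study discontinuation, and SAP 7.4.1 subtracts days of temporary stopping from exposure. SAP 7.3 also trims days after the final bowel movement because they misrepresent balance. No matching rule covers days after the last dose. With 13 to 17 participants one case is visible in a mean, and a rule chosen after the data are seen is open to question.

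**Working it through.** **1. The plan's own figures.** Mo per tablet (SAP 7.3): 95.96 / 432.54 x 15 = 3.328, stated as 3.33 mg; two tablets give 6.66 mg/day. Sample size (SAP 9.1): 13 x 1.25 = 16.25 and 13 / 0.75 = 17.3, consistent with approximately 17. I use n = 13 (completers) and n = 17 (a possible FA Set).

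**2. Off-drug days, last dose Day 8.**
- Days 4-15: Days 9-15 are off drug, 7 of 12. With a 2-day transit allowance, Days 11-15, 5 of 12.
- Days 12-15: 4 of 4.

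A last dose on or before Day 11 leaves no dosed day in the steady-state window.

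**3. Mo balance, Days 12-15.** Assumptions: one compartment, all 6.66 mg/day entering it, the approximately 51 h total Mo half-life of Protocol 4.2, diet ignored.
- k = ln 2 x 24 / 51 = 0.326 per day; fraction kept per day e^-k = 0.7217.
- Amount at the end of day d: A(d) = [A(d-1) + dose(d)] x 0.7217.
- Mean daily balance over Days 12-15 = [A(15) - A(11)] / 4.

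| Last dose | A(11), mg | A(15), mg | Balance, mg/day |
|---|---|---|---|
| Day 15 | 16.79 | 17.14 | +0.09 |
| Day 8 | 6.01 | 1.63 | -1.10 |
| Day 10 | 11.98 | 3.25 | -2.18 |

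Shift of the group mean from one such participant = (stopped - fully dosed) / n:
- Day 8: (-1.095 - 0.087) / 13 = -0.09; / 17 = -0.07.
- Day 10: (-2.183 - 0.087) / 13 = -0.17; / 17 = -0.13.

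With 12 identical fully dosed participants plus the one stopped, the mean goes from +0.09 to about 0.00 (Day 8) or -0.09 (Day 10). That participant alone creates an SD of 0.33 or 0.63 mg/day. With an assumed half-life of 40 to 60 h, the shift at n = 13 is -0.06 to -0.12 (Day 8) or -0.13 to -0.20 (Day 10).

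**4. Cu effect, Days 4-15, one participant with last dose on Day 8.** If off-drug days carry no effect, dilution of the mean = off-drug share / n:
- All off-drug days: (7/12) / 13 = 4.5%; / 17 = 3.4%.
- After the 2-day allowance: (5/12) / 13 = 3.2%; / 17 = 2.5%.

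If the effect instead fades with the 51 h half-life, take the amount on day d as the sum over doses i of 2^(-[24(d-i)+12]/51). The ratio of the stopped to the fully dosed amount, averaged over Days 4-15, gives that participant a loss of 39.7%: 3.1% of the mean at n = 13, 2.3% at n = 17.

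**5. What is protected.** Under SAP 6.4 such a participant should drop out of the PP run of the primary analysis. Two cautions apply. SAP 7.4.1 measures compliance against days expected to be taken, which is undefined after a mandated stop. Protocol Table 6 defines the PP Set without a dosing-compliance condition. Net Cu balance, steady-state Mo/Cu balance and Mo excretion have no PP run.

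**The case against.** The strongest reply is that the case is inferred, rare and small.

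- **Inferred.** Protocol 7.1 keeps the participant for safety follow-up and refers to the Schedule of Activities. It does not say that intake and output collection continues off drug. This stands: continued contribution is the default reading of Protocol 8.2.4.1, not an explicit statement.
- **Rare.** Protocol 7.1 describes permanent stopping as rare, dosing is supervised with mouth checks (Protocol 6.4), and Protocol Table 3 places transaminase elevations usually at 3-6 weeks, beyond the 15-day course. This stands, and no rate can be derived.
- **Small.** One participant moves the mean Mo balance by 0.09 to 0.17 mg/day, or 1.4% to 2.6% of the 6.66 mg daily Mo dose. The model is also crude: Protocol 4.2 says drug that does not form the tripartite complex is hydrolysed and excreted in urine. If half the Mo entered the slow pool (an assumption) and the rest left the same day, the stopped values halve to about -0.55 and -1.09.
- **Visible anyway.** Individual daily balances are plotted (SAP 7.3.2), stopping reasons are listed (SAP 7.1.1), and nothing is tested (SAP 7.3.1.4). A washout profile would be seen, but it would still be in the reported mean.

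A reader might also infer that a group suspension could put 6 of 13 participants off drug and dilute the Cu mean by 19-27%. The documents do not support that as a planning case: Protocol 6.6.1.3 and 6.6.1.6 require an approved amendment before the study continues after a suspension, so the plan would be reopened. Nor do they support calling the primary endpoint unprotected, given its PP run.

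**Conclusion.** The gap is real and modest. As written, the SAP sets no rule for balance data after the last dose, and on the default reading a participant in washout is counted as being at steady state. The weak spot is the Days 12-15 Mo/Cu summary, where neither a PP run nor a sensitivity analysis would show the effect; net Cu balance is exposed in the same way but less.

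Under the stated one-compartment assumptions, one such participant is enough to take a mean Mo balance that is close to zero to about zero or just below it. Those figures illustrate scale and are not predictions: they depend on the half-life, the share of Mo entering the pool, the day of stopping and a frequency that the documents do not give. For Cu, 2.5-4.5% is an upper range for one participant stopping after Day 8.

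It would be tempting to conclude that the FA as-observed primary analysis is wrong and should be made supportive. It should not. Protocol 9.4.1.1 specifies that analysis, and whether to replace it is a matter of choice of estimand, not an error.

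**What to change.** Amend the SAP before database lock:

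1. **Steady state.** In SAP 7.3, limit the Days 12-15 Mo/Cu summary to participants dosed without interruption through Day 15, and list the others separately.
2. **Primary and key secondary endpoints.** Keep the FA as-observed Days 4-15 analysis as primary. Add a supportive on-treatment version for net Cu balance and the other key secondary balance endpoints, using either the PP Set as defined in the SAP or days up to the last dose plus a stated fecal transit allowance. The allowance must be written out, because the existing Day 16-17 provision is optional and covers only steady-state Mo.
3. **Dropout rule.** Have SAP 7.3.1.1 state how data after the last dose are handled when the participant stays in the study.
4. **Record.** Enter these in SAP 4.1 as additions to the protocol analyses; it currently declares no changes.

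Cost: a few sentences, one or two extra tables, and possibly slightly fewer participants in the steady-state mean. A cut at the last dose can also leave an average of only a few days for someone who stops early, so the number of days should be shown. No dose, stopping rule or collection procedure changes.

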6.3. Full Analysis Set

All participants who received at least 1 dose of ALXN1840. The primary analysis will be performed using the Full Analysis (FA) Set.

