9. APPENDICES

9.1. Sample Size, Power, and Randomization

The study sample size is not based on null hypothesis significance testing. A sample size of 13 participants was selected based on convention for this type of study (Strickland, 1971). To accommodate a 25% dropout rate, approximately 17 participants will be enrolled and will receive study drug to achieve 13 evaluable participants who complete the study.

Randomization is not applicable. This is an open-label study in which all participants are expected to receive the same dose of ALXN1840.

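### A participant who leaves during dosing or about the first week after it enters the Days 1-30 total Mo balance as a truncated average, so Mo not yet excreted shows as positive balance

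*SAP*

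**What the plan says.** SAP 7.3 defines Mo balance as Mo input, counting the Mo in ALXN1840, minus Mo output in urine and feces. It states that "The average daily Cu and Mo balance, and/or change from Baseline in average daily Cu and Mo balance will be calculated" over a list of periods. The last of these is "Days 1 through Day 30 representing the entire Treatment and Post-treatment Period (total Mo and Cu balance").

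SAP 7.3.2 sets the method for these endpoints: "The secondary continuous endpoints (Cu balance, Mo balance, urinary excretion, etc.) will be analyzed using the same methods described for the primary analysis". It also says "Secondary analyses will be performed using the FA Set", and SAP 6.3 defines that set as "All participants who received at least 1 dose of ALXN1840", with no completeness requirement. The primary method in SAP 7.3.1 is descriptive statistics on observed data with 95% confidence limits for the mean. Its dropout rule, in SAP 7.3.1.1, is "Participants who prematurely discontinue from the study will be included up to the time of discontinuation".

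The only worked denominator is in SAP 7.3. If the last bowel movement of the Day 1-15 period falls on Day 14, the average runs over Days 1-14. Neither document sets a minimum number of days, or a different denominator, for leavers in the Days 1-30 window. SAP 7.3.1.5 plans no sensitivity analysis, and the Per Protocol Set is named only for the primary analysis.

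**The concern.** Collection runs to Day 30 so that elimination after the last dose can be described; Protocol 4.2 hopes that treatment plus the 15-day terminal phase may give a complete Mo balance. A participant who leaves on Day 10 or Day 15 has no washout data. Their average shows how much Mo was on board during dosing. A completer's average shows what remained after washout. One mean that mixes the two drifts toward apparent Mo retention, by an amount that depends on when people happened to leave.

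For Cu the problem is different. There is no unexcreted Cu dose, but a leaver's truncated average weights on-drug days more heavily than a completer's, so the mean mixes treatment and washout in varying proportions.

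The point concerns people who leave the study. Someone who stops ALXN1840 but stays in the unit through Day 30 has a full window.

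**Working it through.** **The plan's own figures.** Mo per tablet: 95.96 / 432.54 × 15 = 3.328 mg, which reproduces the 3.33 mg in SAP 7.3. Enrolment: 13 / 0.75 = 17.3, in line with approximately 17.

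**Inputs from the documents**
- Two tablets daily for 15 days (Protocol Table 5): 2 × 3.33 = 6.66 mg Mo/day, 15 × 6.66 = 99.9 mg in total.
- Total-Mo half-life about 51 h after a single dose, in plasma (Protocol 4.2).
- Bowel transit about 40 h (Protocol 4.1, SAP 4).
- Dropout allowance (SAP 9.1): "To accommodate a 25% dropout rate, approximately 17 participants will be enrolled".

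**Assumptions not in the documents**
- The plasma half-life stands for whole-body loss.
- The absorbed fraction lies between 0 and 1; both ends are shown.
- All drug Mo is eventually excreted in urine and feces.
- Dietary Mo is in balance.
- A leaver's value is divided by days observed, and each participant counts equally.

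**Formulas.** Daily retention factor r = 2^(-24/51) = 0.7217. If all is absorbed, Mo on board at the end of Day L (L ≤ 15) is 6.66 × (r + r² + … + r^L), and after Day 15 it falls by r per day. If none is absorbed, only a dose younger than 40 h is still in the bowel. At the end of a dosing day that is one dose, 6.66 mg; from Day 17 on it is 0. A participant's average is Mo on board divided by L.

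Day 15, all absorbed: 6.66 × 0.7217 × (1 - 0.7217^15) / (1 - 0.7217) = 17.1 mg, and 17.1 / 15 = 1.14 mg/day. None absorbed: 6.66 / 15 = 0.44 mg/day.

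| Last day observed | Mo unexcreted (mg), none to all absorbed | Share of Mo dosed to date | Participant's average (mg/day) | Mean of 17 with four such leavers (mg/day) |
|---|---|---|---|---|
| 10 | 6.66 to 16.6 | 10 to 25% | 0.67 to 1.66 | 0.16 to 0.39 |
| 15 | 6.66 to 17.1 | 7 to 17% | 0.44 to 1.14 | 0.10 to 0.27 |
| 18 | 0 to 6.4 | 0 to 6.4% | 0 to 0.36 | 0 to 0.09 |
| 22 | 0 to 1.7 | 0 to 1.7% | 0 to 0.08 | 0 to 0.02 |
| 30 (completer) | 0 to 0.13 | 0 to 0.13% | 0 to 0.004 | not applicable |

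The last column is (13 × completer + 4 × leaver) / 17. For Day 15, all absorbed: (13 × 0.0043 + 4 × 1.143) / 17 = 0.27.

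**One leaver.** A single Day 15 leaver among 14: (13 × 0.0043 + 1.143) / 14 = 0.09 mg/day if all is absorbed, and 0.444 / 14 = 0.03 if none is.

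**Sensitivity to half-life (all absorbed).** With 24 h to 96 h in place of 51 h, a Day 15 leaver contributes +0.44 to +2.17 mg/day and a completer 0.000 to 0.081. The mean of 17 with four Day 15 leavers is 0.10 to 0.57. The direction does not change.

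**Weighting alone does not cure it.** Pooling by person-days, four Day 15 leavers give (13 × 0.129 + 4 × 17.14) / (13 × 30 + 4 × 15) = 0.16 mg/day. Nor does reading the label total as a cumulative sum: the leaver's 6.66 to 17.1 mg is still positive balance.

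**The case against.** The dropout rule sits under the Cu primary analysis and reaches Days 1-30 Mo only through a general sentence in SAP 7.3.2, which uses the listed periods as appropriate. Division by days observed and equal weight are nowhere stated for leavers. That is true. They are the natural reading of the Day 14 example and of unweighted summaries of observed data, and no other rule is offered.

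The window also carries limited weight. The secondary Mo balance endpoint in SAP 5.2.2 is balance at steady state, which SAP 7.3 places on Days 12-15, and the endpoint for disposition through the post-treatment period is stated as amounts quantified. Nothing is tested. This stands, and it limits the importance of the point.

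Existing outputs would reveal leavers: summaries by day and by period with n, median, minimum and maximum (SAP 7), individual daily balance plots (SAP 7.3.2), and discontinuation listings (SAP 7.1.1). With 13 completers among 17, the median would be a completer's value in this model. These displays expose the problem but do not correct the reported Days 1-30 mean or its confidence limits.

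The 25% allowance should not be read as four people gone by Day 15. It concerns completing the study, which under Protocol 4.4 includes the last scheduled procedure, the Day 43 visit; someone lost after Day 30 has a full window. Protocol 7.2 expects withdrawal to be uncommon, and the synopsis allows replacement. Four leavers on Day 15 is therefore an upper-end case.

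Finally, restricting to people observed through Day 30 conditions on retention and departs from the Full Analysis Set named for secondary analyses. That is a real cost of the remedy.

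**Conclusion.** The point holds for the Days 1-30 Mo mean. As written, participants who leave during dosing or about the first week after it push that mean toward apparent retention. Under the stated assumptions the mean is up to about 0.09 mg/day with one Day 15 leaver among 14, and 0.10 to 0.27 mg/day with four among 17, where completers alone would give about 0. The sizes depend on the assumed kinetics; the direction does not depend on the exact half-life.

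Some stronger readings are tempting, but the documents do not support them:
- **That most of the drug is still on board when a participant leaves.** In this model it is about 7 to 17% of Mo dosed to date at Day 15.
- **That the true balance is known to be near zero.** Complete excretion is assumed here; recovery is what the study sets out to describe. The healthy-rat study in Protocol 2.1 accounted for about 87% of an intravenous dose over 7 days.
- **That Cu is distorted by a known percentage.** The documents give no time profile for the Cu effect, so no size can be derived.
- **That the main results are at risk.** The Days 4-15 Cu primary endpoint and the Days 12-15 steady-state Mo endpoint are not affected by this mechanism.

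This is worth correcting in the SAP, in proportion to a descriptive secondary summary.

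**What to change.** In SAP 7.3 or 7.3.1.1, state two things before database lock:

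1. The Days 1-30 total Mo and Cu balance is summarised for Full Analysis Set participants with intake and output collection through Day 30. Earlier leavers are not averaged into it.
2. All Full Analysis Set participants, including leavers up to their last day, are shown as cumulative Mo and Cu balance by study day, with n at each day. For Mo, the balance is also given as a percentage of drug Mo administered to date.

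The rule for the Days 4-15 primary analysis can stay as it is. The cost is a sentence or two and one table or plot from data already collected. The downside is that the Days 1-30 mean rests on fewer participants, about the 13 completers the study is sized for, and conditions on staying to Day 30. The cumulative display keeps the leavers' data in view.
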